3.4. Discussion of Study Design, Including the Choice of Control Groups

For Parts A and B of the study, a sequential-cohort, ascending-dose design has been chosen for safety reasons as GB1211 is in the early stages of clinical development, with Part A of the study being the first time it will be administered to humans. Oral doses have been chosen for all parts of the study, as this is the intended clinical route of administration. A 2-part design has been chosen for the food-effect arm, as this gives a within-subject assessment of the influence of food on the PK of GB1211 and so increases the power of the study for the given number of subjects.

It is the intent of Part B to dose subjects such that steady-state plasma levels of GB1211 are achieved and maintained for several days. Based on the available nonclinical data, it is expected that this will be achieved following 9 days of BID dosing; however, a full review of all the safety, tolerability, and PK data from Part A will be performed to confirm the dose regimen for Part B. The dose regimen will comprise no less than once every day and will not exceed 4-times-daily dosing. The dosing duration will comprise no fewer than 7 consecutive days and will not exceed 14 consecutive days of dosing.

Conducting the initial single- and MAD in healthy subjects mitigates the potential confounding effects of the disease state and concomitant medications.

For Part C, it is the intent to dose subjects with suspected NASH and liver fibrosis to investigate safety, tolerability, PK, and the effect on specified exploratory biomarkers following multiple oral doses of GB1211 in subjects of the targeted indication. Preclinical toxicology data provides evidence for dosing over 42 days for Part C, and a study by Mudaliar et al., indicates that decreases in serum markers of fibrosis were observed following 6 weeks administration of obeticholic acid in NAFLD patients⁷; however, a full review of all the safety, tolerability, PK, and emerging exploratory biomarker data from Parts A and B will be performed to confirm the dose regimen for Part C.

Details of the dosing regimen and duration used for Parts B and C of the study will be documented in the TMF.

Based upon the nonclinical data, the duration of each treatment period is considered adequate to achieve the study objectives. Where applicable, an interval of at least 7 days between treatment periods in the food-effect arm is considered adequate to prevent carryover of GB1211; however, may be adjusted based on emerging PK data.

This study will be double-blind and placebo-controlled in order to avoid bias in the collection and evaluation of data during its conduct. Placebo has been chosen as the control treatment to assess whether any observed effects are treatment-related or simply reflect the study conditions.

Continuous 12-lead ECG monitoring will be included in this study in order to explore potential GB1211 effects on the QT interval, with a view of supporting a potential thorough QT study waiver.

3.4.1. Dose Interval

Following thorough review of all available nonclinical data (pharmacological and toxicological), dosing at each dose level in Part A will be such that 2 subjects (1 GB1211 and 1 placebo) will be dosed 24 hours before the remaining 6 subjects. After dosing the first 2 subjects on a separate day, a minimum of a 5-minute dosing interval for the remaining 6 subjects in each dose-ascending cohort is considered acceptable. Continuation to dose the remaining 6 subjects will be at the Investigator's discretion.

For Part B, sentinel dosing is not planned as the total daily dose administered will not exceed a dose shown to be safe and well tolerated in Part A. In addition, accumulation is not expected based on the available nonclinical data and therefore, predicted total daily exposure

in Part B will not exceed a well-tolerated exposure in Part A. However, following review of data in Part A, sentinel dosing may be introduced for Part B cohorts, if exposure is predicted to exceed the maximum exposure in Part A.

3.5. Selection of Doses in the Study

In the 42-day repeat oral dose toxicology studies, NOAELs in the mouse and the dog were 500 mg/kg/day and 50 mg/kg, respectively, corresponding to human equivalent doses (HEDs) of 40 and 27 mg/kg, respectively. Therefore applying a 10-fold safety margin the maximum recommended starting dose (MRSD) is 2.7 mg/kg, approximately 162 mg for a 60 kg subject. In vitro data in human cells suggests an IC₅₀ of GB1211 of 0.1 µM (0.5 µg/mL) supporting the chosen MRSD.

In the PD study⁶ evaluating the effect of GB1211 in carbon tetrachloride-induced liver fibrosis in mice there was no pharmacological activity observed at 2 mg/kg but there was activity at 10 mg/kg. Therefore the MRSD that is not considered to be pharmacologically active, based on the 2 mg/kg dose level, is 0.16 mg/kg, equivalent to approximately 9.6 mg in a 60 kg subject. The lowest pharmacologically active dose has been defined as 10 mg/kg, representing a HED of 48 mg for a 60 kg subject.

The proposed starting dose of 5 mg is 1.9-fold lower than the MRSD of 9.6 mg (based on the PD study⁶) and therefore is not expected to have any pharmacological activity.

The proposed IMP dose levels for the study are shown in [Table 3](#). As described in [Section 3.6](#) each dose following the starting dose may be subject to change based on review of data from previous cohorts.

Table 3: Proposed Investigational Medicinal Product Dose Levels

Study Part	Cohort	Subject Numbers	Treatment Period 1	Treatment Period 2
Part A	A1	101 – 108	5 mg or placebo (fasted)	
	A2	109 – 116	20 mg or placebo (fasted)	
	A3	117 – 124	50 mg or placebo (fasted)	50 mg or placebo (fed)
	A4	125 – 132	100 mg or placebo (fasted)	
	A5	133 – 140	200 mg or placebo (fasted)	
Part B	B1	201 – 211	TBD	
	B2	212 – 222	TBD	
Part C	C1	301 - 325	TBD	

Abbreviation: TBD = to be determined

For Part B of the study, dose levels, dosing frequency/interval, and dosing duration will be fully decided, in consultation with the Sponsor, on the basis of data from Part A of the study. For Part C of the study, dose levels, dosing frequency/interval, and dosing duration will be fully decided, in consultation with the Sponsor, on the basis of data from Part A, and at least 1 Part B cohort. The total daily dose of GB1211 administered during this part of the study will not exceed the maximum well-tolerated dose level studied in Part A.

Dose levels should not increase by more than 5-fold for predicted nonpharmacologically active dose levels and by 3-fold for predicted pharmacologically active dose levels.

The highest dose level may exceed the top dose shown in the above table, providing systemic exposure does not exceed that stated in the dose escalation stopping criteria ([Section 3.7](#)).

Details of all doses administered in Parts A, B, and C of the study will be documented in the TMF.

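### Does the mis-converted in-vitro IC50 in Protocol Section 3.5 undermine the dose-escalation plan?

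*Protocol*

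**What the plan says.** Protocol Section 3.5 builds the dose rationale in three layers.

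- **Toxicology.** From the mouse and dog NOAELs, "the maximum recommended starting dose (MRSD) is 2.7 mg/kg, approximately 162 mg for a 60 kg subject". The next sentence gives the in-vitro IC50 "of GB1211 of 0.1" µM, with a mass equivalent of "0.5 µg/mL) supporting the chosen MRSD". This is the only use made of the IC50.
- **Mouse fibrosis study.** No activity was seen at 2 mg/kg, so the starting-dose ceiling without expected activity "is 0.16 mg/kg, equivalent to approximately 9.6 mg in a 60 kg subject". The active end is also defined: "The lowest pharmacologically active dose has been defined as 10 mg/kg, representing a HED of 48 mg for a 60 kg subject". The 5 mg starting dose is then described as not expected to be active.
- **Escalation limit.** "Dose levels should not increase by more than 5-fold for predicted nonpharmacologically active dose levels and by 3-fold for predicted pharmacologically active dose levels". Table 3 plans 5, 20, 50, 100 and 200 mg for Part A.

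Section 1.3 gives the only other molar and mass pair for the compound: a hERG IC50 of 5.06 µM, equated to 2700 ng/mL.

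**The concern.** The two molar-to-mass pairs describe the same compound but imply molar masses of 534 and 5000 g/mol, so they cannot both be right. If the molar half of the IC50 is correct, the printed mass concentration is about ten times too high. A reader comparing it with plasma levels in ng/mL would then be inclined to judge too many exposures inactive.

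That seems to matter because predicted activity decides which fold limit applies. The step from 5 to 20 mg is 4-fold: allowed under the 5-fold limit, not under the 3-fold one. Section 3.5 never labels 20 mg in words, and the dose lies between the 9.6 mg and 48 mg figures. In a first-in-human trial, a potency error beside a step that depends on the activity label could mean that the planned escalation breaks the protocol's own rule.

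**Working it through.** **1. Unit conversion.** Inputs: 5.06 µM and 2700 ng/mL (Section 1.3); 0.1 µM and 0.5 µg/mL (Section 3.5).

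- Implied molar mass: 2700 / 5.06 = 533.6 g/mol. Allowing for rounding, 2650 / 5.065 = 523 to 2750 / 5.055 = 544.
- 0.1 µM × 533.6 g/mol = 53.4 ng/mL = 0.053 µg/mL.
- Gap: 500 / 53.4 = 9.4-fold (9.2 to 9.6 over the molar-mass range).
- In reverse: 500 / 533.6 = 0.94 µM.
- If 0.1 and 0.5 are themselves rounded to one figure, the gap runs from 450 / (0.15 × 533.6) = 5.6 to 550 / (0.05 × 533.6) = 20.6. Rounding does not close it.

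The size is consistent with a misplaced decimal point (0.05 against 0.5), but that does not prove which half is wrong.

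**2. Does any figure depend on the IC50?** Every dose figure in Section 3.5 reproduces without it. The conversion factors are those the section implies: mouse 40/500 = 0.08, dog 27/50 = 0.54.

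| Figure | Source | Arithmetic |
|---|---|---|
| 2.7 mg/kg, 162 mg | dog NOAEL | 50 × 0.54 = 27; 27 / 10 = 2.7; × 60 = 162 |
| 9.6 mg | inactive mouse dose | 2 × 0.08 × 60 = 9.6 |
| 48 mg | active mouse dose | 10 × 0.08 × 60 = 48 |
| 1.9-fold margin at 5 mg | 9.6 mg figure | 9.6 / 5 = 1.92 |

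The exposure limits in Section 3.7 (Cmax 19755 ng/mL, AUC 52486 ng.h/mL) match the average of the male and female mouse NOAEL values in Section 1.4: (17005.0 + 22506.6) / 2 = 19755.8, and (46617.4 + 58355.9) / 2 = 52486.65. They do not use the IC50 either.

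**3. The escalation steps.** 20/5 = 4.0; 50/20 = 2.5; 100/50 = 2.0; 200/100 = 2.0. The SAP treatment list (Section 7) adds 400 mg, and 400/200 = 2.0. Every step but the first meets even the 3-fold limit, however the doses are classified.

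For 5 to 20 mg, the rule does not say whether the dose left or the dose reached sets the limit.

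- Dose left: 5 mg is stated not to be expected to be active, so the 5-fold limit applies and 4-fold is within it.
- Dose reached: 20 mg is 20/48 = 0.42 of the defined lowest active dose. Against that threshold it is below the active range, the 5-fold limit applies again, and 4-fold is within it.

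A breach needs the second reading and also a rule that anything above 9.6 mg counts as active. The 9.6 mg figure is the human equivalent of a mouse dose at which nothing was seen; the section does not present it as the point where activity begins.

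**The case for a change.** The strongest case for the concern is that this is the only human-cell potency figure in the dose rationale, and that the mass value is in the form a dose-review team would set beside emerging plasma concentrations. Up to three further cohorts may be added to each part (Section 3.3), and doses may go above Table 3, so the rationale stays in use after the first cohort. Meanwhile 20 mg is 20/9.6 = 2.1 times the figure for which inactivity is supported, and no sentence classifies it.

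Two parts of this stand. The conversion is wrong by the protocol's own figures, and a sentence classifying 20 mg and saying which dose sets the fold limit would have been clearer.

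The link between the two does not stand. Neither Section 3.5 nor Section 3.6 compares a predicted or observed human concentration with the IC50, so the error has no stated route to a dose classification. Correcting the IC50 would leave the 20 mg question where it is, and that question exists without the IC50. Escalation is also controlled by sentinel dosing in each Part A cohort, by safety and PK review with at least 4 subjects on active drug, and by exposure limits. None of these refers to the IC50.

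**Conclusion.** This is a clerical slip of about 9.4-fold in a supporting remark, together with a small gap in labelling. Sections 1.3 and 3.5 contradict each other on the conversion and must be reconciled against the source data. Whichever half is corrected, no stated dose, fold limit, stopping criterion or analysis changes. The planned 4-fold step is not shown to break the protocol's limit, and the later steps meet the tighter limit in any case.

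The conclusion rests on two assumptions. The hERG pair, the only available cross-check, is taken as correctly converted; if it were the faulty one, the IC50 would still enter no calculation. And the 48 mg figure is read, as Section 3.5 words it, as the threshold for predicted activity. This note takes no position on which doses or step limits are appropriate.

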3.6. Dose Escalation

Doses will be administered in an escalating manner following satisfactory review by the Sponsor and Investigator of the safety and tolerability data (up to 48 hours post-final dose) and PK data (up to 24 hours post-final dose) from the lower dose levels. Doses may be reduced and may be lower than the starting dose. There will be a minimum of 10 days between dose escalations to allow sufficient time for an adequate safety review.

Dose escalation in both Parts A and B will only occur if data from a minimum of 6 and 7 subjects, respectively, have been reviewed from the previous lower dose cohort, such that data from a minimum of 4 subjects who have received GB1211 will be used to make the dose escalation decision.

The justification for this is as follows:

- Based upon nonclinical data, no clinically important off-target effects are expected within the proposed dose range.
- A minimum of 4 subjects receiving the active drug is considered sufficient to characterise the safety profile and PK response to GB1211.

Between each dose escalation, the Investigator will review all available blinded data to ensure it is safe to proceed with the planned dose escalation. An interim safety report, summarising results from all available safety assessments, will be sent to the Sponsor prior to the start of each successive cohort. Any clinically significant results will be discussed with the Sponsor before dose escalation continues. Interim PK data will also be reviewed in terms of dose escalation and to confirm that the study design remains appropriate. In the event of a disagreement between Sponsor and Investigator on the dose escalation decision, the decision of the Investigator will be upheld.

3.7. Dose Escalation Stopping Criteria

The study will be halted if 1 or more subjects experience an serious adverse event (SAE) that is considered to be related to IMP or 2 or more subjects experience severe AEs that are considered to be related to IMP. If, following an internal safety review, the Sponsor deems it appropriate to restart the study; this can be done following approval of a substantial protocol amendment.

In Parts A and B, following consultation with the Sponsor, dose escalation will stop if:

- One or more subjects in a cohort experience an SAE that is considered to be related to IMP or 2 or more subjects in a cohort experience severe AEs that are considered to be related to IMP.
- Clinically relevant signs or symptoms of similar nature occur in 2 or more subjects in a cohort that, in the opinion of the Investigator, warrant stopping of dose escalation.
- There is evidence of clinically significant increases in liver function tests (aspartate aminotransferase [AST], ALT, alkaline phosphatase, bilirubin, and/or gamma-glutamyl transferase), defined as 3 times the upper limit of normal (ULN) in 2 or more subjects in a cohort (confirmed with repeat testing), which are considered related to the IMP in the opinion of the Investigator.
- QT interval corrected for heart rate using Fridericia's method (QTcF) increases > 60 msec compared to baseline (predose) and/or absolute QTcF values > 500 msec (confirmed by repeat measurement) in 2 or more subjects in a cohort.
- The systemic exposure for any individual subject is predicted to exceed a C_{max} of 19755 ng/mL and/or an AUC from time zero to 24 hours postdose (AUC_{0-24}) of 52486 ng.h/mL; ie, systemic exposure will be no greater than the lowest exposure at the NOAEL (Criterion is based on preclinical toxicology data from both male and female mice, where no gender differences were observed in terms of safety findings).

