1.4. Summary of Toxicology

As detailed in Section 4.3 of the IB⁶, repeat-dose toxicity studies were conducted in 2 species, the CD-1 mouse and Beagle dog:

- In 2 mice repeat-dose toxicity studies, there were no GB1211-related deaths.
 - In a non-GLP study, there were no significant findings in mice given single escalating oral doses up to 500 mg/kg, or daily oral doses at 500 mg/kg/day for 14 days. No effects on body weights, food consumption, clinical pathology, organ weights, or macroscopic or microscopic findings were observed. Systemic saturation was observed at doses > 50 mg/kg/day.
 - In the 6-week GLP study (doses of 50, 150, and 500 mg/kg/day), there were no GB1211-related deaths. However, there were 10 deaths in total, with 4 animals sacrificed in moribund condition with eye-related changes, 3 were due to gavage errors (2 were sacrificed moribund, 1 was found dead), and the cause of 3 deaths was not determined (1 was sacrificed moribund due to clinical observations and 2 were found dead). Additional details for these deaths can be found in the IB⁶ (Section 4.3.2.1.2). No GB1211-related, adverse effects were observed (no effects on clinical signs, ophthalmic observations, body weights, food consumption, clinical pathology parameters, organ weight, or macroscopic or microscopic pathology were observed in the dosing or recovery periods). The no observed adverse effect level (NOAEL) was 500 mg/kg/day, which corresponded to maximum observed plasma concentration (C_{max}) values of 17005.0 and 22506.6 ng/mL, and area under the plasma concentration-time curve (AUC) from zero to the time of the last quantifiable concentration ($\text{AUC}_{0-\text{tlast}}$) values of 46617.4 and 58355.9 ng·h/mL, for males and females, respectively, on Day 42 (Table 1).

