- In 2 dog repeat-dose toxicity studies, systemic saturation was observed at doses > 50 mg/kg. No GB1211-related adverse effects were observed. Increases in QT and QT interval corrected for heart rate (QTc) intervals noted in males at 15 or 50 mg/kg/day and females at 50 mg/kg/day were not considered adverse because the range of individual QT values were within what would be considered the normal range for the dog. The left bundle branch block (LBBB) noted in one female at 50 mg/kg/day (1 hour postdose in Week 6) is not a normal variation in dogs, however, as it was present during the predose phase collection for this animal, it was not considered to be GB1211 related (*Covance study 8377741 – to be published*). In addition, no electrocardiogram (ECG) findings were observed in telemeterized dogs given up to 50 mg/kg in the cardiovascular safety pharmacology study. The NOAEL was 50 mg/kg/day, which corresponded to C_{\max} values of 27047.0 and 17789.9 ng/mL, and $AUC_{0-t_{\text{last}}}$ values of 117585.2 and 63452.2 ng·h/mL, for males and females, respectively, on Day 42 (Table 2).

In addition, there was no genotoxic potential for GB1211 in appropriately conducted assays in bacteria (reverse mutation test), human lymphocytes (in vitro micronucleus test), and in mouse bone marrow (in vivo micronucleus test).

No developmental and reproductive toxicology studies have been conducted so far.

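### The exposure limit for stopping escalation and individual dosing is the male/female mouse average at the NOAEL, not the lowest NOAEL exposure as claimed, and lies 13% (AUC) to 16% (Cmax) above the protocol's lowest values

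*Protocol*

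**What the plan says.** Section 3.7 of the protocol ends its list of escalation stops with an exposure rule. Escalation stops when the predicted Cmax of any one subject goes above 19755 ng/mL, or the predicted AUC0-24 above 52486 ng.h/mL. The protocol explains what the two limits are meant to secure: "systemic exposure will be no greater than the lowest exposure at the NOAEL". It then gives their source in a parenthesis: "Criterion is based on preclinical toxicology data from both male and female mice, where no gender differences were observed in terms of safety findings". Section 4.8 uses the same two figures and the same claim to stop a subject's dosing permanently, but without the parenthesis.

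The limit is also used elsewhere. Section 3.3 allows added cohorts only within it. Section 3.5 allows doses above the planned top dose "providing systemic exposure does not exceed that stated in the dose escalation stopping criteria".

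The underlying animal data are in Section 1.4, as Day 42 results at each species' NOAEL, males then females:

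- Mouse Cmax: "values of 17005.0 and 22506.6 ng/mL".
- Mouse AUC0-tlast, in ng.h/mL: "values of 46617.4 and 58355.9".
- Dog Cmax: "values of 27047.0 and 17789.9 ng/mL".
- Dog AUC0-tlast, in ng.h/mL: 117585.2 and 63452.2.

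Table 1 repeats the mouse figures. Table 2 repeats the dog AUC figures but not the dog Cmax figures.

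**The concern.** The mean of two unequal values cannot be the smaller of them. If the limits are sex averages, male mice at their NOAEL had lower mean exposure than the limit, and the assurance attached to it is not met. An investigator or ethics reviewer reading 3.7 or 4.8 would believe that no subject is allowed beyond the lowest exposure seen at a NOAEL, when the figures allow somewhat more.

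This is the protocol's only absolute numerical exposure limit. Part B has a further restriction, but that one is relative to exposure in Part A. The absolute limit governs four decisions: escalation, individual stopping, added cohorts, and going above the planned 200 mg. The last has practical relevance, because SAP Section 7 lists a 400 mg treatment and SAP Section 10.4.2 analyses a range up to 400 mg.

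**Working it through.** **Inputs** (protocol Section 1.4; Day 42, at the NOAEL)

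| | Male | Female |
|---|---|---|
| Mouse Cmax, ng/mL | 17005.0 | 22506.6 |
| Mouse AUC0-tlast, ng.h/mL | 46617.4 | 58355.9 |
| Dog Cmax, ng/mL | 27047.0 | 17789.9 |
| Dog AUC0-tlast, ng.h/mL | 117585.2 | 63452.2 |

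Limits in Sections 3.7 and 4.8: Cmax 19755 ng/mL; AUC0-24 52486 ng.h/mL.

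**Step 1. Reproduce the limits.** Arithmetic mean of the two sexes in mice:

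- Cmax: (17005.0 + 22506.6)/2 = 39511.6/2 = 19755.8
- AUC: (46617.4 + 58355.9)/2 = 104973.3/2 = 52486.65

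With the decimals dropped, these are the stated limits, digit for digit.

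**Step 2. Rule out other origins.**

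- Mouse geometric means, √(male × female): 19563.4 and 52157.5. No match.
- Lowest mouse values: 17005.0 and 46617.4. No match.
- Dog arithmetic means: (27047.0 + 17789.9)/2 = 22418.45 and (117585.2 + 63452.2)/2 = 90518.7. No match.

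**Step 3. Compare the limits with the lowest NOAEL exposures.** Across both species and sexes, the lowest values on both measures are those of male mice.

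- Cmax: 19755/17005.0 = 1.162, or 16.2% above (difference 2750 ng/mL)
- AUC: 52486/46617.4 = 1.126, or 12.6% above (difference 5868.6 ng.h/mL)

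Female dogs also fall below the Cmax limit: 19755/17789.9 = 1.110, or 11.0% above. They do not fall below the AUC limit (52486/63452.2 = 0.827).

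As an illustration, a subject predicted at a Cmax of 18500 ng/mL would be within the limit, yet above the mean Cmax of both male mice and female dogs at their NOAELs.

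**Step 4. Check the tables.** Table 1 agrees with the text for mice. Table 2 gives Day 42 dog Cmax at 50 mg/kg as 102302.0 (male) and 79036.9 (female). These are identical to its Day 1 AUC0-tlast entries at that dose, and they disagree with the 27047.0 and 17789.9 in Section 1.4, which cites Table 2. The table cells look like a transcription error. Someone checking the limit against Table 2 alone would see dog Cmax far above it and miss the female dog value. The mouse result does not depend on this.

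The limit is also expressed as AUC0-24, whereas the animal values are AUC0-tlast. The protocol does not comment on the difference.

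**The case against.** The best defence is that lowest refers to species. With the sexes pooled, mice have lower mean exposure than dogs on both measures (19755.8 against 22418.45, and 52486.65 against 90518.7). The parenthesis in 3.7 points to pooled sexes, and Section 1.5 reports no sex differences in mouse pharmacokinetics. On this view the figures are right and the wording is merely loose. This is probably how the figures arose. But neither section says that they are averages or that the comparison is between species. The parenthesis speaks of safety findings by sex, and 4.8 omits it altogether.

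A second argument is that the consequence is small. The NOAEL was the top dose in both 6-week studies, so animals without compound-related adverse effects reached exposures above the limit. Examples are female mice on Day 42 (22506.6 and 58355.9) and male dogs (27047.0 and 117585.2). Male mice at 150 mg/kg on Day 42 had an AUC of 52541.3, above both the limit and the 46617.4 at 500 mg/kg. The low male value therefore partly reflects less-than-proportional exposure and is not a toxicity boundary. Other safeguards apply as well: the serious adverse event, liver and QTcF stops, the limits on dose steps, and the relative exposure limit in Part B. All of this stands. It bears on how much harm the gap could do, not on whether figure and sentence agree.

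It is also fair to say that the male mouse figures are themselves group means, so any limit of this kind can exceed some individual animals. That the rule is applied to individual subjects does not by itself decide between one average and another. The contradiction lies between the averaged figure and the protocol's own claim.

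Finally, the dog Cmax comparison rests on the value in the text of 1.4, since the table disagrees and the source report is not available here.

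**Conclusion.** The concern holds. The limits are the male/female mouse means at the NOAEL with decimals dropped, and they exceed the lowest NOAEL exposures in the protocol by 16.2% for Cmax and 12.6% for AUC. The assurance in 3.7 and 4.8 is therefore untrue as written.

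This rests on the Day 42 mouse values, which agree between Section 1.4 and Table 1, and on reading lowest literally across the sex-specific results. The additional 11.0% for female dog Cmax assumes that the text of 1.4 is right and Table 2 is wrong. The AUC comparison treats AUC0-tlast as comparable with AUC0-24, as the protocol itself does.

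The documents contain no human exposure data, so it cannot be said whether any subject would fall between the lowest NOAEL values and the limits, or that the present limits are unsafe. The point needs correcting because a numerical threshold with several operative uses contradicts its own definition.

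**What to change.** Reconcile the two limits with the sentence that defines them and with the NOAEL exposures in Section 1.4 and Tables 1 and 2. Either the figures change to match the claim, or the claim changes to say what the figures are, including the species, the averaging over sexes, and the AUC measure used. Put the same figures and the same explanation in 3.7 and 4.8. Sections 3.3 and 3.5 then follow, because they refer back to the stopping criteria. Correct the Day 42 dog Cmax cells in Table 2 against the source report.

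The choice of limit belongs to the sponsor's toxicology and safety team, and none is proposed here.

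The cost is a protocol amendment covering two paragraphs and one table, with no extra subjects or procedures. If the figures are changed to match the claim, the limit becomes somewhat more restrictive.
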